4.1.3 The Per-Protocol Population (PP)

The Per-Protocol (PP) analysis set will include only those subjects of either given treatment arm defined as the treatment actually received at the start of the study, and will consist of subjects who met all the inclusion criteria, none of the exclusion criteria, were successfully treated with an index procedure, had no important protocol deviations, and attended the scheduled follow-up visits (did not miss more than one mandatory Holter recording, and TTM compliance >50%).

The PP analysis set will also be used to evaluate endpoints already evaluated using the mITT as the primary analysis set, thus serving as supportive analyses to that of the mITT efficacy analysis.

4.2 PRIMARY ENDPOINT

Freedom from documented AF, 12 months after a single index ablation procedure to be understood as a single AF ablation procedure (i.e. including redo procedures for non-AF indications).

4.2.1 **Hypotheses**

Freedom from documented AF after 12 months will be higher in the tailored group than the anatomic group.

The null and alternative hypotheses are as follows:

$$H_0: S_1(t) = S_2(t)$$

$$H_A: S_1(t) > S_2(t),$$

where S1(t) and S2(t) represent the survival functions for the Tailored and Anatomical arms, respectively, at any given time t.

4.2.2 Sample Size

The primary endpoint is freedom from AF, 12 months after a single ablation procedure. Assuming that 62% of the Subjects in the anatomic group will be free from AF at the end of follow-up1,2, that at least 77% of the Subjects of the tailored group will be free from AF at the end of follow-up (i.e., Hazard Ratio (HR) 0.547), then 292 Subjects (146 in each group) are required to show that time to AF is significantly different between groups (Log-Rank test for a one-sided superiority trial, significance level α =0.025, statistical power of 80%, under the assumption that the hazard rates are proportional). Assuming a drop-out rate of 22% (no index ablation performed or loss to follow up), 374 Subjects are required overall (187 in each group). Following 50% of subjects having a primary endpoint collected, the sample size will be re-estimated using the Mehta-Pocock conditional power (CP) approach.

4.2.3 **Primary Analysis**

The primary endpoint will be analyzed using a Cox Proportional hazards model to conduct a time-to-event comparison (of hazard rates from risk of AF recurrence at a time t) between the Tailored (treatment) and Anatomical (control) groups. The model will include an indicator for group (study arm), a dichotomous effect for AF duration (persistent AF \geq 6 months; persistent AF \leq 6 months), and applying right-censoring of subjects lost to follow-up. The model will be used to estimate the hazard ratio of AF occurrence between the Tailored arm compared to that of the Anatomical arm, along with a two-sided 95% CI and p-value for the HR on behalf of the group predictor. The actual null hypothesis of the Primary Endpoint will

be tested with a one-sided Log-Rank test at a significance level of α =0.025. The null hypothesis will be rejected if the p-value is < 0.025, and the survival distribution of the Tailored arm will be considered superior relative to that of the Anatomical arm. All of the outputs described above will be generated under the same single Cox Proportional hazards model, which will be conducted in the mITT population. A Kaplan-Meir plot will be generated to visually display the survival distributions of the Tailored and Anatomical arms, respectively to accommodate the p-value from their comparison.

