4.3.1 Secondary Analysis

The secondary endpoint analyses will consist of the following:

Two tests of the primary endpoint in the mITT population, but expanded to be defined as freedom from AF/AT, with or without AADs, 12 months after one or two procedures. A superiority hypothesis will be tested using a Cox proportional hazards model with randomization group, AF duration, and AF/AT strata as fixed effects, with a one-sided alpha level of 0.025:

Both analyses under will be evaluated according to the following hypotheses:

$$H_0$$
: $S_1(t) = S_2(t)$

$$H_A$$
: $S_1(t) > S_2(t)$,

where $S_1(t)$ and $S_2(t)$ represent the survival functions for the Tailored and Anatomical arms, respectively, at any given time t. If the null hypotheses for each of the tests is rejected, the following superiority statements will be considered on behalf of each endpoint:

- 1. Tailored ablation is superior to anatomical with respect to freedom from AF/AT, with or without AADs, 12 months after one or two procedures.
- 2. Tailored ablation is superior to anatomical with respect to freedom from AF/AT, with or without AADs, 12 months after one procedure.

Similarly to the primary endpoint analyses, Cox Proportional hazards regression models will be fit and assessed for goodness-of-fit. Then to test each null hypothesis, one-sided Log-Rank Tests will be. Just like under the primary analysis, the p-value from the one-sided Log-Rank Test run under each Cox Proportional hazards model will ultimately be what is used to either reject (p < 0.025) or fail to reject ($p \ge 0.025$) the null hypotheses above. Both Cox models will be conducted in the mITT population.

Kaplan-Meier plots will be generated for each endpoint, to visually display the differences among the survival distributions of the Tailored and Anatomical arms, respectively, with each plot accommodated by the p-value generated from their respective one-sided Log-Rank test.

3. The composite adverse event (AE) rate defined as the number of AEs per month occurring in each treatment arm from time of index procedure through to 12-month follow-up, where composite AEs are defined by either death, a cerebrovascular event, or any serious procedure-related adverse event, will be conducted. in the Safety population (see Section 4.5, Safety Endpoints below).

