4.4.1 Exploratory Endpoint Analysis

Endpoints 1-8 will be tested using a Cox proportional hazards model with randomization group and AF strata as fixed effects. Hypotheses will be tested in the following order, and each at a less stringent one-sided alpha level of 0.05, given the exploratory nature of these analyses)

Endpoint 9 will be tested by comparing the QoL score at each visit between tailored and anatomical ablation using a t-test for difference in means. A Shapiro-Wilks test will be used to assess whether the data meets normality assumptions for parametric. Should the normality assumption be violated, a non-parametric method such as the Wilcoxon test will be used instead. The effect of time will also be assessed using a generalized linear mixed model for repeated measures.

Endpoints 10 - 21 and 23 will be tested by comparing tailored and anatomical ablation groups. using a t-test for differences in means. Should the normality assumption be violated, a non-parametric method such as the Wilcoxon test will be used instead.

Endpoint 22 will not undergo any statistical analysis, but the data collected (blinded baseline voltage maps prior to ablation) will be provided to the sponsor in a dataset / spreadsheet format to enable any post-hoc analysis that may be desired.

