6.5 RANDOMIZATION

After successful enrollment, the patient will be automatically randomized in a 1:1 ratio to one of two arms through the eCRF system: "Anatomical" arm (PVI) or "Tailored" arm (Dispersion + smart-PVI). Randomization will be stratified in order to balance the treatment arms in terms of subjects with persistent AF (< 12 months) and long-standing persistent AF (≥ 12 months). Subjects will not be informed of their randomization assignment.

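### SAP 4.2.3 does not fix a single deciding primary test, and the 12-month randomisation factor is in neither the test nor the model

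*SAP*

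**What the plan says.** SAP 4.2.3 makes three statements about the primary analysis.

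- A Cox model supplies the hazard ratio, its two-sided 95% confidence interval and a p-value for the group term: "The model will include an indicator for group (study arm), a dichotomous effect for AF duration", cut at 6 months.
- The null hypothesis is to "be tested with a one-sided Log-Rank test at a significance level of" 0.025. No strata or covariates are attached to that test.
- "All of the outputs described above will be generated under the same single Cox Proportional hazards model", in the mITT population.

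For the two secondary survival endpoints, SAP 4.3.1 says that "the p-value from the one-sided Log-Rank Test run under each Cox Proportional hazards model will ultimately be what is used" and likens this to the primary analysis. Its model is fitted "with randomization group, AF duration, and AF/AT strata as fixed effects". The exploratory survival endpoints in SAP 4.4.1 use a model "with randomization group and AF strata as fixed effects". Neither strata term is defined.

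SAP 6.5 describes the allocation: "Randomization will be stratified in order to balance the treatment arms in terms of subjects with persistent AF (< 12 months") against long-standing persistent AF of 12 months or more. Protocol 5.3.2 gives the same split but limits it to Europe.

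**The concern.** A log-rank test can be read off a Cox model only if arm is the sole covariate. Once the 6-month term is in the model, an ordinary log-rank cannot be one of its outputs. Read strictly, SAP 4.2.3 leaves two candidates: the ordinary log-rank, or the score test for arm from the 6-month-adjusted model. Read loosely, it also admits a log-rank stratified at 6 months or the Wald test of the group term. Two analysts could follow the same text and reach different deciding p-values, and the reported confidence interval could contradict the superiority decision.

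Separately, the 12-month factor used to allocate patients is absent from both the test and the model, and the 6-month term captures it only in part. No reason is given for the change of cut-point, although the SAP uses 12 months in the subgroups (4.2.6), exploratory endpoint 6 (4.4), the interim rates by AF type (6.1) and the geographic poolability check (6.4).

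**Working it through.** **1. The planned sample size.** SAP 4.2.2 gives 62% and 77% free from AF, one-sided 0.025 and 80% power, and says 292 patients "are required to show that time to AF is significantly different between groups (Log-Rank test for a one-sided superiority trial".

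- HR = ln(0.77)/ln(0.62) = 0.547.
- A log-rank noncentrality calculation (exponential survival, 12 months of follow-up, no strata) gives power 0.8002 at N = 292 and 0.7975 at N = 290, so 292 is reproduced.
- Expected events: 292 × (0.38 + 0.23)/2 = 89.
- With 22% dropout: 292/0.78 = 374.4, against 374 stated.

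The trial was therefore sized for an ordinary log-rank.

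**2. Why the two statements conflict.** At each event, let p be the share of the risk set in the Tailored arm. The log-rank is Z = Σ(g − p)/√Σp(1 − p), which is the score test of the arm-only Cox model (ties aside). With a 6-month term x and fitted coefficient γ, p becomes Σg·exp(γx)/Σexp(γx) over the risk set. The variance becomes I_gg − I_gx²/I_xx. The two statistics coincide only if γ is zero and arm is unrelated to x in the risk sets.

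**3. What the other sections say.** SAP 4.2.2 and Protocol 6.2 and 6.5.1 point to the ordinary log-rank. SAP 4.2.5 points the other way: it lists the model without AF duration as an additional analysis, so the main analysis is taken to be adjusted. SAP 3 says the SAP prevails, so the protocol cannot settle it.

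**4. Size, by simulation.** Design inputs are as in step 1. The following are assumptions, because the documents do not give them:

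- prognostic hazard ratios for AF duration of 6–12 and ≥12 months, each against <6 months;
- permuted blocks of 4 within the 12-month strata, constant hazard, and complete follow-up to 12 months;
- two case mixes (<6 / 6–12 / ≥12 months): A = 40/45/15%, from the quota minimums in the protocol synopsis, and B = 25/45/30%, assumed.

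There were 20,000 trials per scenario and mix.

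| Assumed HRs (6–12, ≥12) | (1,1) | (1,2) | (1,3) | (1.5,2) | (2,3) |
|---|---|---|---|---|---|
| Log-rank vs 6-month Cox CI disagree, A (%) | 1.1 | 1.5 | 2.4 | 2.9 | 5.2 |
| Same, B (%) | 1.2 | 1.8 | 3.0 | 2.6 | 4.1 |
| Power, 12-month-stratified minus ordinary log-rank, A (points) | +0.1 | +1.0 | +2.8 | +0.3 | +0.8 |
| Same, B | 0.0 | +1.3 | +3.6 | +0.4 | +0.9 |
| Power, 12-month-stratified log-rank minus 6-month score test, A | 0.0 | +0.8 | +2.6 | −0.3 | −0.8 |
| Same, B | +0.1 | +1.1 | +3.0 | 0.0 | −0.2 |

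- The standard error of the disagreement rates is at most 0.16 points. Repeat runs with separate code gave 4.4 to 5.4% for (2,3) in mix A, so that entry is best read as about 5%.
- A further simulation, with hazard ratios of 1.0, 1.5 or 2.0 at each cut-point, gave 1.2 to 6.0%.
- The two strict readings of the deciding test disagree in 1.0 to 5.2% of trials.
- Among trials with log-rank p between 0.01 and 0.05 (19–22% of trials), test and interval disagree in 5.8 to 23.2%.
- A matched pair nearly removes the problem: 0.3–0.5% for log-rank and Cox both stratified at 12 months, and 0.4–0.5% for the unstratified log-rank with the arm-only Cox model.

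**5. Type I error and the interim.** At fixed N, type I error is 2.1–2.6%. With the SAP 6.1 increase simulated (mix A, three scenarios, read as 100 extra patients, so 392), it is 2.0–2.6% for every combination of interim and final statistic. If the best of five candidate tests were picked afterwards, rejection under the null would be 3.0–3.3%. SAP 6.1 does not say which model supplies the interim hazard ratio. At HR 0.547, the decision to increase N differs between the log-rank and the 6-month Cox model in 3.8, 6.5 and 10.9% of trials for (1,1), (1,3) and (2,3).

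**The case against.** The strongest reply is that the SAP does say which test decides: a log-rank with nothing attached, matching the sample size, the protocol and a null hypothesis that does not condition on AF duration. On that view a single careless sentence pulls the other way. An adjusted hazard ratio beside an unadjusted test is common, and SAP 4.2.5 already plans the arm-only Cox model. This has weight, and it is why the minimum remedy is enough to cure the ambiguity. It does not remove the conflict, because SAP 4.3.1 repeats the same construction and SAP 4.2.5 treats the adjusted analysis as the main one.

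A second reply is that omitting a stratification factor is a matter of preference here. That is largely fair: no type I inflation appears, and power gains are small, depend on assumed effects and are slightly negative in some comparisons. Stratifying now would also split on the AF type for which SAP 6.1 sends per-arm interim rates to senior management, so the timing of the choice must be shown.

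Third, the protocol limits stratified randomisation to Europe and the SAP does not. The difference is real. US patients all have AF under 12 months, so the factor is still known for every patient, but a pooled stratum may not copy the actual allocation strata exactly.

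Finally, every disagreement figure above roughly 1% rests on assumed prognostic effects, and the simulation ignores losses and the ties created by counting early repeat procedures at 3 months.

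**Conclusion.** The concern holds. SAP 4.2.3 does not define a unique deciding test, SAP 4.3.1 carries the fault to both secondary survival endpoints, and the randomisation factor is in neither the primary test nor the primary model. The effect is modest. Conflicting conclusions arise in about 1% of trials if AF duration has no prognostic effect and in roughly 5 to 6% if it is strongly prognostic, mostly when the p-value is near 0.025. These figures rest on the assumptions listed in the check. The sample size is unaffected. The case is for fixing one test in advance; it does not rest on gaining power or on error inflation. The SAP should be corrected before the arms are compared.

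**What to change.** Delete the sentence tying all outputs to one Cox model in SAP 4.2.3 and the parallel wording in 4.3.1, and name one matched pair that alone decides.

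- **Preferred:** a one-sided 0.025 log-rank stratified by AF duration (<12 vs ≥12 months, US patients in the <12 stratum), with the hazard ratio and 95% confidence interval from a Cox model stratified the same way.
- **Minimum:** state that the log-rank is unstratified, as in the sample-size calculation, and report beside it the arm-only Cox hazard ratio already planned in SAP 4.2.5.

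Keep the 6-month and log-duration models as sensitivity analyses. Define the strata terms in SAP 4.3.1 and 4.4.1, state which statistic is or was used for conditional power in SAP 6.1, and list the change in SAP 7.

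Fix the choice before the final comparison. The documents do not say whether the interim preceded SAP 1.4 (February 2024). If it has been run, record when the choice was made and that it was made without the per-arm rates by AF type. If that cannot be recorded, use the minimum option, which only clarifies the test already named.

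The minimum option costs wording only. The preferred option adds a STRATA statement to the analysis programs. AF duration is collected at enrolment, so neither option needs new data or patients.

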4.2.4 Sensitivity Analyses of Primary Endpoint

The Primary Endpoint Analysis will additionally be conducted in the PP population.

4.2.5 Other analyses on primary endpoint

Primary analyses will be repeated with the following changes in the Cox Proportional Hazards model:

Without AF duration fixed effect. With AF duration fixed effect numerically expressed as the logarithm of the AF duration (in months) instead of the categorical definition. The format of the AF duration variable (dichotomous vs. numerically expressed as the log of months) will be compared between the models with which each is fit.

4.2.6 Subgroup Analyses

The following subgroup analyses will be performed following the approach described for the primary analysis:

- 1. All subjects with AF duration within the following categories: < 6 months, ≥ 6 months, < 12 months, and ≥ 12 months
- 2. AF presentation at index procedure (spontaneous AF, induced AF)
- 3. With/without AADs
- 4. Patient gender (male and female)

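### The SAP repeats the one-sided primary analysis in ten overlapping subgroups with no treatment-by-subgroup interaction and no rule for interpretation, so chance differences in significance could be read as subgroup effects.

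*SAP*

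**What the plan says.** SAP 4.2.6 opens: "The following subgroup analyses will be performed following the approach described for the primary analysis". It then lists four factors. The first is AF duration: "All subjects with AF duration within the following categories: < 6 months, ≥ 6 months, < 12 months, and ≥ 12 months". The others are AF presentation at the index procedure (spontaneous or induced), "With/without AADs", and gender. That gives 4 + 2 + 2 + 2 = 10 subgroups. The AF-duration categories overlap one another, and each factor cuts across the others.

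The approach referred to is in SAP 4.2.3. It is a Cox model with arm and AF duration dichotomised at 6 months, giving an HR with a two-sided 95% confidence interval, together with a Kaplan-Meier plot. The null hypothesis is to "be tested with a one-sided Log-Rank test at a significance level of" 0.025, and the decision rule reads: "The null hypothesis will be rejected if the p-value is < 0.025, and the survival distribution of the Tailored arm will be considered superior" to the Anatomical arm.

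Section 4.2.6 contains no arm-by-subgroup interaction, multiplicity statement, exploratory label or rule for interpretation. The only treatment interaction in either document is arm-by-site, judged at p<0.15, in SAP 6.4; the regional poolability check there refers back to it. SAP 4.4.1 tests AF of less than 1 year and AF of 6 months or more again (exploratory endpoints 6 and 7), at one-sided 0.05, also without an interaction.

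**The concern.** Whether the treatment effect differs between subgroups is a question about a difference between two hazard ratios. Separate tests within each level do not answer it. A smaller level has fewer events and can miss significance while its hazard ratio equals that of the larger level. When many subgroups are tested, one may also cross the threshold by chance.

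The results are likely to be used. The SAP introduction says that its analyses may go into manuscripts and regulatory submissions. AF duration is also built into the design, through enrolment minimums and a narrower US population (protocol 5.2.1). A non-significant result in long-standing AF, or a significant one in a single stratum after a failed primary test, could be read as evidence about who benefits.

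**Working it through.** **Inputs from the documents.** Freedom from AF 62% against 77%, HR 0.547, one-sided alpha 0.025, power 80%, 292 patients before drop-out, 22% drop-out, 374 in total (protocol 6.2, SAP 4.2.2). At least 60% with AF of 6 months or more and at least 15% with 12 months or more (protocol 5.2.1).

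**Inputs assumed.** Neither document gives shares for AF presentation, AAD use or gender. I took induced AF at 15-50%, the second AAD level at 30-50% and women at 25-50%. AF-duration shares (<6, 6 to <12, ≥12 months) were 40/45/15%, which sit at the protocol minimums, or 30/40/30%. Factors were taken as independent of one another.

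**The plan's own figure.** HR = ln(0.77)/ln(0.62) = 0.547. A Lakatos log-rank calculation with exponential survival gives 80.02% power at 292 patients and 79.75% at 290, so 292 reproduces. Drop-out: 292/0.78 = 374.4, in line with 374. Expected events: 292 × (0.38 + 0.23)/2 = 292 × 0.305 = 89.

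**Power within a subgroup if the HR is 0.547 everywhere.** Schoenfeld: power = Φ(|ln HR| × √d / 2 − 1.96), where d = 89.06 × share.

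| Share | Events | Power |
|---|---|---|
| 15% | 13.4 | 20% |
| 25% | 22.3 | 30% |
| 40% | 35.6 | 44% |
| 50% | 44.5 | 52% |
| 60% | 53.4 | 60% |
| 75% | 66.8 | 69% |
| 85% | 75.7 | 75% |

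**Chance that the two levels disagree.** The levels of one factor are disjoint, so P(disagree) = p1(1 − p2) + p2(1 − p1).
- 15:85 split: 0.196 × 0.253 + 0.747 × 0.804 = 0.65
- 25:75 split: 0.296 × 0.307 + 0.693 × 0.704 = 0.58
- 40:60 split: 0.437 × 0.403 + 0.597 × 0.563 = 0.51
- 50:50 split: 2 × 0.521 × 0.479 = 0.50

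A two-sided interaction test at 0.05 signals a difference in about 5% of such trials. Across the five splits (AF duration at 6 and at 12 months, presentation, AADs, gender), a simulation of 100,000 trials gave at least one discordant pair in 89-90%. It gave at least one interaction p<0.05 in about 22%.

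**No effect anywhere.** If the ten tests were independent, 1 − 0.975^10 = 22% would show at least one p<0.025. Allowing for overlap, the simulation gave 14.7-14.8% across the share scenarios. In about 12% of trials this happened while the overall test was not significant.

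**Power of the interaction test.** For a true ratio of hazard ratios of 0.547, power = Φ(|ln 0.547|/SE − 1.96), with SE = √(4/(89.06f) + 4/(89.06(1 − f))). This gives 30% for f = 0.50, 23% for f = 0.25 and 17% for f = 0.15.

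**The AF-duration covariate.** The 6-month indicator is constant in the <6-month and ≥6-month subgroups, and also in the ≥12-month subgroup, because everyone there is also ≥6 months. It varies only in the <12-month subgroup.

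**The case against.** The strongest defence is that 4.2.6 makes no subgroup claim. The decision rule in SAP 4.2.3 is tied to the null hypothesis of the primary endpoint. Where the SAP intends further superiority statements it writes them out, as in 4.3.1 for the secondary endpoints; none is written for subgroups. Hazard ratios with confidence intervals are already part of the inherited approach. This stands. A reader might infer that the plan will declare superiority within subgroups, but the text does not say so. The supportable criticism is that 4.2.6 carries over the test and is silent on how to read it.

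Two other stronger readings fail. A reader might infer that the constant AF-duration term stops the model from being fitted, or helps to produce chance findings. It does neither: the term cannot be estimated and drops out, while the arm hazard ratio and an unadjusted log-rank p-value are unchanged. SAP 4.2.5 already includes a model without that term. A reader might also infer that the trial's type I error is inflated. The subgroups do not enter the primary decision, so it is not.

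It is also fair to say that an interaction test is weak here, as shown above. That limits what the remedy can detect, but it does not justify comparing significance between levels.

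**Conclusion.** The concern holds as a matter of interpretation. The planned method gives no direct comparison between subgroups, and under a uniform effect its significance results would differ between the levels of a factor in about half to two-thirds of trials. A non-significant result in the ≥12-month subgroup is the expected outcome at the protocol minimum share, even if the treatment works equally well there. The 15% figure is a floor, and a larger share would raise the power.

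The no-effect figures, about 15% overall and about 12% alongside a failed primary test, rest on assumed shares for presentation, AAD use and gender, though varying them barely moves the result. All figures use large-sample approximations, which are rough at 13 events.

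The constant AF-duration covariate is a separate, minor specification gap affecting three subgroups. A further gap is that 4.2.6 does not say when AAD use is measured. The protocol has these drugs stopped before ablation, allowed for 3 months afterwards and discouraged later (protocol 5.3.3 and the post-procedure medication part of 5.3.4). The split may therefore be a post-randomisation grouping, not a baseline one.

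**What to change.** Reword SAP 4.2.6 as follows.

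- For each baseline factor, fit one Cox model in the full mITT set with arm, factor and arm-by-factor interaction. The factors are AF duration split at 6 months, AF duration split at 12 months, AF presentation and gender. Include AAD use only if it is defined at baseline.
- Report subgroup hazard ratios with 95% confidence intervals and the interaction p-value.
- Label these analyses exploratory and state that no superiority conclusion will be drawn within a subgroup.
- As a separate tidy-up, omit the 6-month covariate from the AF-duration subgroup analyses.

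The cost is SAP wording and a few lines of code, with no new data. The text should acknowledge that interaction power is low, and that up to five unadjusted interaction tests give at least one p<0.05 about 22% of the time when there is no true difference. Emphasis should therefore fall on the estimates and their intervals, not on the interaction p-values.
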